**【 2020/12/14 】**

## Design

This was a 4-week randomized, parallel, single-blind and sham-controlled trial, followed by another 4-week open-label intervention, to investigate the feasibility and efficacy of iTBS over the bilateral pSTS in children and adolescents with ASD at Chang Gung Memorial Hospital (CGMH, Linkou, Taiwan). There were 2 phases in this RCT, with one-month follow-up. Specifically, after baseline assessments, participants were randomized to the Active or Sham group (Phase 1, Baseline-Week 4). Given limited human resources, the investigator ([name]) and his assistant assessed and delivered rTMS to all participants. Therefore, only participants and their caregivers were blind to the treatment condition (single-blind). Active versus sham iTBS was administered over the pSTS 2 days/week for 4 weeks. Entering Phase 2 (Week 5-8), participants were unblinded, and then active iTBS over the pSTS were administered to all participants 2 days/week for the other 4 weeks. This distinct design allowed for a conventional rigorous RCT of low risk of bias (Phase 1), and concomitantly resolved a potential inequity issue by providing access to iTBS for every participant (Phase 2) (Green, 2008). This also enabled investigating effects of longer treatment courses. Considering the feasibility based on their school activities, participants freely chose 2 intervention days, which are at least 48 hours apart from each other, from Monday to Saturday in the beginning of their interventions. Once they made the choice, the schedule of sessions was fixed throughout the trial.

Clinical assessments were completed in participants within one week of the first iTBS session of Phase 1 (Baseline) and Phase 2 (Week 5), following the last iTBS session (Week 8), as well as at follow-up (Week 12). With the same baseline and follow-up assessment schedule, social cognition was specifically measured within 1 hour following the last iTBS session of Phase 1 and 2, respectively.

A minimum total sample size of 68 was estimated using G\*Power 3.1 (Faul, Erdfelder, Buchner, & Lang, 2009), being powered (90% power and two-sided 5% significance) to detect a standardized effect at 0.4 from within-between interaction of the repeated-measure ANOVA model. The estimated effect size was guided using the pool effect on social behavior deficits in existing studies (Barahona-Correa et al., 2018).

Before implementation, this study was approved by the Research Ethics Committee at CGMH (104-9413A) and registered with ClinicalTrials.gov (NCT03621189). The procedures and purpose of the study were explained face-to-face to participants and their parents, who then provided written informed consents.

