## Outcomes

The primary outcomes included the safety profiles, as well as the social deficits as measured by the caregiver-rated Social Responsiveness Scale (SRS) (Gau, 2013), since theoretically targeting the pSTS is aimed to modulate the activity within the social brain network. Atypical social cognition is often associated with the autistic symptoms. The secondary outcomes thus included two common tasks assessing the social cognition performances of people with ASD (Barahona-Correa et al., 2018), i.e., the Reading the Mind in the Eyes test (RMET) (Baron-Cohen, Wheelwright, Hill, Raste, & Plumb, 2001; T. S. Li et al., 2020) and Frith-Happe Animations Task (White, Coniston, Rogers, & Frith, 2011) (Barch et al., 2013). Notably, these two tasks, nonetheless, are not specific to the pSTS activities. Given our preliminary beneficial results in compulsory behaviors in adults (Ni et al., 2017), we also adopted the Repetitive Behavior Scale-Revised (RBS-R) (Bodfish, Symons, Parker, & Lewis, 2000; Y. C. Yang et al., 2019) as the exploratory outcome. Higher scores on the SRS and RBS-R represent greater severity of the two domains of autistic symptoms. RMET total scores represent how many correct mental states the participant has inferred from the eyes, indicating

individual's theory of mind capability. Frith-Happe Animations also tap mentalizing capacity by asking the participant to infer whether interaction intents exist between two triangles. When the participant answered about the presence/absence of interactions, he/she was further asked to select words that best described how these triangles were feeling at the end of each video clip. Participants scored 1 point for correct answers to either presence/absence or exact description of mental states, which are summarized as the total Categorical scores and Feelings scores, respectively. To enhance a contrast and reduce assessment time, we adopted the revised Frith-Happe Animations following those used in the Human Connectome Project (Barch et al., 2013), which only included social and random interactions.

Side effects were assessed immediately after each session and at one-month follow-up using open-ended questions inquiring any physical discomfort and then close-ended questions including "pain at application site", "headache/dizziness", "tinnitus" and "anxiety" experienced during and after iTBS

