### Statistics

Herein we only reported clinical and cognitive data during RCT. Independent t-test and chi-square test were used to evaluate the difference of baseline characteristics. To simultaneously examine the immediate effect of pSTS vs. sham stimulation in different visits, the generalized estimating equations (GEE) model was conducted using the data of Baseline, Week 4, and Week 8. To account for correlations between individuals' repeated measurements between visits, a working correlation matrix with a first-order autocorrelation was used with the robust estimator of standard error. Treatment, Time, and a two-way interaction (Active vs. Sham  $\times$  Time) effects were modeled in the GEE. The maximum likelihood method in the GEE was used to address the missing values from dropouts. In consideration of high inter-individual variability in the clinical symptoms and social cognitive function at baseline, we also implemented an additional analysis using the symmetrized percentage change (Ayers, 2006) to investigate the iTBS effects. Because there was significant difference for both groups at baseline in the RMET, all of the analyses in the GEE and symmetrized percentage change were adjusted.

To comprehensively examine effects across time for both conditions, exploratory within-group comparisons were also conducted in the same GEE regardless of whether the main effect was statistically significant. However, when the main effect of GEE is not statistically significant, the significant findings in these exploratory within-group comparisons should be interpreted conservatively. The correction for multiple comparisons was implemented to avoid type-I errors. Five pairwise within-group comparisons (i.e., Baseline vs. Week 4, Baseline vs. Week 8, Baseline vs. Week 12,

Week 4 vs. Week 8, Week 8 vs. Week 12) were calculated separately in Active (8-week active TBS) and Sham (4-week sham followed by 4-week active TBS) groups.

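### Disclosing Phase 1 allocation on entry to Phase 2 is not needed for universal access, and it exposes the Week 8 caregiver-rated SRS contrast to expectations that differ by arm

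*Combined protocol and SAP*

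**What the plan says.** In Phase 1, according to the Design section, "only participants and their caregivers were blind to the treatment condition (single-blind"; the investigator and assistant who deliver and assess are not masked. On entry to Phase 2 "participants were unblinded, and then active iTBS over the pSTS were administered to all participants 2 days/week for the other 4 weeks", and that phase is described as open-label. The section gives Phase 2 an equity purpose, namely that it "concomitantly resolved a potential inequity issue by providing access to iTBS for every participant (Phase 2", and adds a scientific one: "This also enabled investigating effects of longer treatment courses".

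The Outcomes section names, next to safety, "social deficits as measured by the caregiver-rated Social Responsiveness Scale (SRS" as the primary efficacy outcome. The Statistics section says the GEE "model was conducted using the data of Baseline, Week 4, and Week 8", with Treatment, Time and their interaction. Five within-arm comparisons, some involving Week 12, are "calculated separately in Active (8-week active TBS) and Sham (4-week sham followed by 4-week active TBS) groups".

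**The concern.** Fair access and disclosure of allocation are separate things. For fair access, everyone must receive active iTBS in Phase 2 and know it. What each child received in Phase 1 can stay undisclosed without affecting access.

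Disclosure matters because the caregiver scores the SRS. Once allocation is known, one group of caregivers has learned that the first four weeks were sham, and the other that they were active. Fresh hope in the first group, or satisfaction or disappointment in the second, can move the ratings by arm. The knowledge that Phase 2 is active is common to both arms and largely cancels in a between-arm difference. Knowledge of the Phase 1 allocation does not cancel.

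Two uses of the data are affected: the Week 8 arm difference, which is the randomised evidence on course length, and the interaction test, which draws on Week 8 as well as the masked Week 4 contrast. The shift could mimic or hide a benefit of the longer course.

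**Working it through.** **1. What each visit compares, and what the families know.**

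| Visit | Active arm has had | Sham arm has had | Between-arm test planned? | Do families know Phase 1 allocation? |
|---|---|---|---|---|
| Week 4 | 4 weeks active | 4 weeks sham | Yes (GEE) | Meant to be masked |
| Week 8 | 8 weeks active | 4 sham + 4 active | Yes (GEE) | Yes |
| Week 12 | as Week 8, plus follow-up | as Week 8, plus follow-up | No, within-arm only | Yes |

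Week 8 is therefore the only planned between-arm contrast of 8 with 4 weeks of active treatment, and it comes after disclosure. The alternative, the change from Week 4 to Week 8 within the Active arm, has no concurrent control for natural course or repeat rating.

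**2. The plan's own figure.** The Design section gives a minimum total of 68 for a standardised effect of 0.4, 90% power and two-sided 5%. For the within-between interaction, λ = f²·N·m/(1−ρ), with df1 = (k−1)(m−1) and df2 = (N−k)(m−1). The document does not state m or ρ. Taking k = 2, f = 0.4/2 = 0.2, m = 2 and ρ = 0.5 gives λ = 0.04 × 68 × 2/0.5 = 10.88 on 1 and 66 df, and power 0.9015. So 68 is reproduced. This point does not change it; it only supplies 34 per arm, assuming equal allocation.

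**3. Illustration of size.** Assumptions: a standalone two-sample comparison at Week 8, 34 per arm, outcome in SD units, normal approximation. The disclosure-driven shift b is assumed to be 0.2 to 0.4 SD, because the documents give no figure.

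- SE = √(2/34) = 0.2425.
- b/SE = 0.2/0.2425 = 0.82 and 0.4/0.2425 = 1.65.
- With no true difference, the rejection rate is P(Z > z − b/SE) + P(Z < −z − b/SE), with z = 2.576 at the plan's 0.01 level and 1.960 at 0.05.

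| Shift b (SD) | Rejection rate at 0.01 | Rejection rate at 0.05 |
|---|---|---|
| 0 | 1% | 5% |
| 0.2 | 4.0% | 13.1% |
| 0.4 | 17.7% | 37.8% |

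- If the longer course were truly better by 0.5 SD (assumed) and the shift ran against it, the net differences would be 0.5, 0.3 and 0.1 SD for shifts of 0, 0.2 and 0.4. Power at 0.01 would be 30%, 9% and 2%.

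These figures compare full bias with none, not with the bias that would remain after the fix. They also do not describe the Treatment by Time GEE itself.

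**The case against.** The case on the other side is substantial.

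- **The trial appears to be finished.** The text is in the past tense, reports a baseline imbalance in the RMET, and says findings have been fed back to families. Masking cannot then be restored, and the Design section must not be rewritten to describe something that was not done. This stands. It limits the remedy to analysis and reporting, but does not make the rule sound.
- **Phase 2 is openly unmasked and subsidiary.** The claim of low risk of bias is attached to Phase 1 only, course length gets a single sentence, and the within-arm comparisons are called exploratory, with a caution when the main effect is not significant. This is fair. However, the caution does not mention unmasking, and Week 8 sits in the main between-arm model.
- **Withholding allocation would not fully mask.** Former sham participants move from a tilted coil at 60% AMT to active stimulation at 80% AMT and may notice a difference, and the staff know the allocation. This stands: the change would reduce the bias, not remove it.
- **The shift is assumed.** This also stands. Baseline power of 30% for a 0.5 SD difference further shows that this contrast is weak even without bias.

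Three stronger readings are tempting, and the documents do not support them. A reader might infer that the whole longer-course question rests on caregiver ratings. It does not: the RMET and the animations task are performance tests and are less exposed, although those taking them are unmasked too. A reader might infer that a planned Week 12 arm comparison is spoiled, but none is specified. A reader might also infer that the masked Phase 1 result is contaminated, because "Clinical assessments were completed in participants within one week of the first iTBS session of Phase 1 (Baseline) and Phase 2 (Week 5". The documents do not say whether that rating came before or after disclosure, so this is an open question and not a finding.

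**Conclusion.** The point holds as a design weakness that was cheap to avoid. Disclosing Phase 1 allocation served neither stated purpose of Phase 2. It lets arm-specific expectations into the Week 8 SRS contrast, and so into the interaction test. The direction of any bias is unknown and its size cannot be derived from the documents; the 0.2 to 0.4 SD range is illustrative only.

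The conclusion rests on one inference. The text says that participants were unblinded and does not mention caregivers. That caregivers also learned the allocation is a strong inference, since they were the other masked party, the patients are aged 8 to 17, and the phase is open-label. The argument about what access requires depends on no number.

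**What to change.** **If disclosure has not yet occurred, or for a future trial:** in the Design section, state that families are told all Phase 2 sessions are active, and that Phase 1 allocation is not disclosed to participants or caregivers until after the Week 12 assessment, except for a safety need.

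**If disclosure has already occurred:** leave the description of what was done as it is, and in the Statistics section and the report:

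- base the efficacy conclusion on the Week 4 contrast alone, and state whether the SRS rating used for it preceded disclosure;
- report the Week 8 SRS arm difference as an unmasked comparison of 8 with 4 weeks of active iTBS;
- do not present the Week 4 to Week 8 change within the Active arm as evidence on course length;
- state explicitly whether caregivers were told the allocation.

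**Cost.** Prospectively, the change is to the wording of the protocol and the information sheet. The sample size of 68, the visits and everyone's access to active iTBS are unchanged. Families would learn their allocation about 8 weeks later (Week 12 instead of the end of Week 4), and masking would remain imperfect for the reasons given above. Retrospectively, the cost is a narrower efficacy claim and a few sentences of reporting.

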Considering clinical heterogeneity in ASD, we defined responders based on the Reliable Change Index (RCI) calculated using the SRS total scores. The RCI takes into consideration the false positive outcome that could occur due to random error from repeated measurements alone (Jacobson & Truax, 1991). The RCI represents differences in individual's scores between before- and after-intervention, divided by the standard error of the difference of the measure. Responders were those with RCI  $>1.64$ , which corresponds to  $p<0.05$  with one-sided test (i.e., the null hypothesis was that iTBS would not help with social symptoms). Demographic and clinical features were compared between the responders and non-responders using non-parametric tests.

In addition to the stratified analysis based on responsiveness, we also tested a three-way interaction (Active vs. Sham  $\times$  Time  $\times$  Modifier) to explore whether iTBS over the pSTS is more beneficial for individuals with ASD with certain characteristics. Effect modifiers included demographics, intelligence quotient, clinical traits, comorbidity, and medication.

Statistical analysis was performed using the SAS Version 9.4 software (SAS Institute, Cary, NC, USA). Considering multiple comparisons including the clinical symptoms and social cognitive function (5 measurements), the GEE, within-group analyses and three-way interaction were considered statistically significant at  $p\text{-value}\leq0.01$ . Despite contention, herein, alpha level in-between 0.01 and 0.05 were considered a nominal significance for hypothesis generating for the future study (Bays, 2019).

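### The sample size of 68 gives 90% power at two-sided 0.05, but significance is declared only at 0.01, where the same sizing model gives about 74–76%

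*Combined protocol and SAP*

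**What the plan says.** The sample-size paragraph in Design reads "A minimum total sample size of 68 was estimated using" G*Power 3.1, "being powered (90% power and two-sided 5% significance", and the target is "to detect a standardized effect at 0.4 from within-between interaction of the repeated-measure ANOVA model". It does not give the number of measurements, the correlation between them, the effect-size convention or a dropout allowance.

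The analysis in Statistics is a different model: "the generalized estimating equations (GEE) model was conducted using the data of Baseline, Week 4, and Week 8", with a first-order autoregressive working correlation and robust standard errors.

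The decision rule is in the last paragraph of Statistics. It opens "Considering multiple comparisons including the clinical symptoms and social cognitive function (5 measurements", and then says that "the GEE, within-group analyses and three-way interaction were considered statistically significant at" p ≤ 0.01. It adds that "alpha level in-between 0.01 and 0.05 were considered a nominal significance for hypothesis generating". The five measurements are not listed. From Outcomes I take them to be the SRS, the Reading the Mind in the Eyes test (RMET), the two Animations scores and the Repetitive Behavior Scale-Revised. The 0.01 then looks like 0.05/5.

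**The concern.** The sample size was set at one alpha and the conclusion is drawn at another. The rule names the GEE without exception, so the SRS falls under 0.01, and power at that level is stated nowhere.

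A reader of Design will take the risk of missing the planned effect to be 10%. Part of that 90%, however, is the chance of landing between 0.01 and 0.05, which Statistics classes as hypothesis generating. This matters most when the SRS result is null or falls in that band: a null from a trial described as 90% powered looks more conclusive than one from a trial with about 74% power at the threshold it applies.

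**Working it through.** **Inputs from the documents.** Total N = 68; two groups; effect 0.4; power 90%; sizing alpha 0.05, two-sided; decision alpha 0.01.

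**Inputs assumed.** Equal arms; sphericity; 0.4 read as a standardized mean difference, so f = 0.4/2 = 0.2; m = 2 measurements; correlation ρ = 0.5. The last three are varied below.

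**Formula.** For the within-between interaction with two groups, λ = N·f²·m/(1−ρ), df1 = m−1 and df2 = (N−2)(m−1). Power is the probability that a noncentral F(df1, df2, λ) exceeds the central F critical value.

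**Step 1: reproduce 68.** λ = 68 × 0.04 × 2/0.5 = 10.88, with df 1 and 66.
- At 0.05 the critical F is 3.986 and power is 90.15%.
- N = 66 gives 89.26%, so 68 is the smallest even total that reaches 90%.

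**Step 2: change only alpha.** At 0.01 the critical F is 7.035 and power is 73.87%. The gap is 90.15 − 73.87 = 16.28 points.

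**Step 3: check without the ANOVA details.** Starting from exactly 90% at 0.05, the normal approximation is Φ(1.2816 + 1.9600 − 2.5758) = Φ(0.6658) = 74.7%.

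**Step 4: vary the unstated inputs.** With f = 0.2, these are the correlations (in steps of 0.001) for which the smallest even N is 68:

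| m | ρ giving N = 68 | Power at 0.01, N = 68 | Total N for 90% at 0.01 |
|---|---|---|---|
| 2 | 0.498–0.512 | 73.7–75.1% | 96–98 |
| 3 | 0.370–0.388 | 74.4–76.0% | 92–94 |
| 4 | 0.248–0.269 | 74.7–76.4% | 90–94 |

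Overall, power at 0.01 is 73.7–76.4%, and the gap from power at 0.05 is 14.5–16.4 points.

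Settings with much higher power at 0.01 would not have produced 68. For example, m = 3 with ρ = 0.5 gives 86.0% at 0.01, but needs only 56 participants at 0.05.

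Entering f = 0.4 in the same formula needs at most 36 participants (m = 2 to 4, ρ from 0 to 0.79). Under the alternative convention λ = N·f²·(m−1) with m = 2, f = 0.4 gives λ = 68 × 0.16 = 10.88, so the powers are those of Steps 1 and 2.

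**Step 5: number analysed.** For m = 2 and ρ = 0.5:

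| Analysed | Power at 0.05 | Power at 0.01 |
|---|---|---|
| 60 | 86.1% | 66.8% |
| 64 | 88.3% | 70.5% |
| 68 | 90.2% | 73.9% |
| 72 | 91.7% | 77.0% |
| 80 | 94.2% | 82.3% |

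**The case against.** The best defence is that Design is not false. It states the 90% together with its alpha, Statistics prints the 0.01 threshold openly, and the band from 0.01 to 0.05 is disclosed as nominal. On that reading, 90% is the chance of reaching at least the nominal tier. This is right as far as it goes: the fault is a planning figure left unreconciled with the decision rule, and nothing is concealed. But the document does not describe its power that way, and it withholds the word significant from that tier.

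Second, the recalculation describes an ANOVA at 0.01, a test the plan does not run. That stands as a limit on the figures. The power of the three-visit GEE cannot be worked out from the documents, and its interaction also covers Weeks 5–8, when "then active iTBS over the pSTS were administered to all participants". The 74% must therefore not be presented as GEE power. The same limit applies to the stated 90%.

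Third, the G*Power inputs are assumed. That is true, but they are constrained to return the plan's own 68, and within that constraint the answer moves by less than three points.

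Finally, the document is in the past tense, so no sample-size decision appears to be open, and no p-value would change. This is why a change of wording is enough. The 0.01 rule is conservative and does not inflate type I error.

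**Conclusion.** The concern holds. The 90% belongs to alpha 0.05. At the 0.01 level that the plan uses to declare significance, the same sizing model with 68 analysed gives about 74–76%, a shortfall of roughly 15–16 points. Holding 90% at 0.01 would have needed about 90–98 participants in total.

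The result rests on the repeated-measures ANOVA sizing model, on inputs calibrated to return 68, on exactly 68 being analysed, and on the SRS being one of the five measurements. Because 68 is a minimum and Statistics refers to dropouts, the true shortfall could be smaller or larger. The sample-size calculation and the 0.01 rule are each sound taken alone; the error is that their alphas differ. It should be corrected because it affects how a null or nominal SRS result is read.

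**What to change.** Keep the 0.01 threshold and restate the sample-size paragraph in Design, for example:

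> Under the repeated-measures ANOVA sizing model, 68 analysed participants give 90% power at two-sided 0.05 and about 74% at the 0.01 level used to declare significance.

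Recompute the second figure from the G*Power inputs actually used, and state those inputs: effect-size convention, number of measurements and correlation. List the five measurements behind the 0.01 rule. Do not describe either figure as the power of the GEE.

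Do not move the SRS to 0.05 now. The document already reports observed data (the RMET baseline difference in Statistics and the absence of sham guessing in Intervention). Testing the SRS at 0.05 is acceptable only if that was specified before outcome data were seen; otherwise label any such analysis post hoc.

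The cost is wording only: no extra participants and no change of threshold or analysis. The stated power becomes less favourable, about 74% instead of 90% at the level that decides significance.

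### The 90% power for N=68 is stated at two-sided 5%, but the analysis declares significance only at p ≤ 0.01, where the same effect has about 74% power; the metric of the 0.4 effect is not given

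*Combined protocol and SAP*

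**What the plan says.** The sample-size statement is in the Design section: "A minimum total sample size of 68 was estimated" with G*Power, "being powered (90% power and two-sided 5% significance) to detect a standardized effect at 0.4 from within-between interaction" in a repeated-measures ANOVA. On the source of 0.4 it says only: "The estimated effect size was guided using the pool effect on social behavior deficits in existing studies". It does not say whether 0.4 is Cohen's f or a standardised mean difference. It also omits the number of measurements, the within-person correlation, the noncentrality option, the allocation ratio and any dropout allowance.

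The Statistics section plans a GEE with treatment, time and their interaction, "using the data of Baseline, Week 4, and Week 8". Its last paragraph sets the threshold: because five measurements are tested, "the GEE, within-group analyses and three-way interaction were considered statistically significant at" p ≤ 0.01. Results between 0.01 and 0.05 are labelled nominal and hypothesis-generating. The caregiver-rated SRS, named as a primary outcome in the Outcomes section, is not exempted from this threshold.

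**The concern.** The trial is sized at one significance level and judged at another. A result that meets the level used for sizing, say p = 0.03, would not count as significant under the plan's own rule. The probability of success under that rule is therefore lower than the 90% stated.

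The second difficulty is interpretation. A standardised effect of 0.4 said to be guided by a pooled effect is easily read as a mean difference of 0.4 SD. As Cohen's f in a two-group, two-visit interaction it can mean a difference twice as large. Without the metric, a reader cannot tell which benefit the trial was able to detect, and so cannot judge how much weight a null SRS result would bear.

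**Working it through.** **Inputs.** From the Design section: total N = 68, power 90%, two-sided 5%, effect 0.4, two groups. From the Statistics section: threshold 0.01, three visits in the GEE. Assumed because not stated: equal allocation (34 per arm), all 68 analysable, and within-person correlation ρ over a range. The calculation follows the repeated-measures ANOVA named in the Design section, not the GEE.

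**1. Reproducing 68.** With two groups and m = 2 measurements, the interaction is an F test with 1 and N − 2 = 66 degrees of freedom. Two settings return 68:

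- f = 0.4 with noncentrality λ = f²N: 0.16 × 68 = 10.88.
- f = 0.2 with the default λ = f²Nm/(1 − ρ) and ρ = 0.5: 0.04 × 68 × 2 / 0.5 = 10.88.

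The critical value at 0.05 is F = 3.99, and λ = 10.88 gives power 90.15%. At N = 66 the power is 89.3%, so 68 is the smallest even total.

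Other settings do not return 68. For example, f = 0.4 with the default option, m = 2 and ρ = 0.5 needs only 20. The option entered therefore matters.

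**2. What effect this is.** For m = 2 the test is a two-sample comparison of change scores, with λ = d²N/4 and d in SDs of change. Solving, d = √(4 × 10.88 / 68) = √0.64 = 0.8. The smallest difference detectable with 90% power at 0.05 is 0.798.

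**3. The same effect at the plan's threshold.** At 0.01 the critical value is F = 7.04. With λ = 10.88 the power is 73.9%. For 90% at 0.01, d must be about 0.96 (λ = 0.96² × 68 / 4 = 15.7).

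**4. Other routes to 68.** The settings in step 1 are not the only ones. With f = 0.2 and the default option:

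| m | ρ | λ | df | power at 0.05 | power at 0.01 |
|---|---|---|---|---|---|
| 3 | 0.38 | 0.04 × 68 × 3 / 0.62 = 13.2 | 2, 132 | 90.5% | 75.3% |
| 4 | 0.25 | 0.04 × 68 × 4 / 0.75 = 14.5 | 3, 198 | 90.1% | 74.9% |

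The loss from 0.05 to 0.01 is almost the same whichever of these routes was used.

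**5. If 0.4 is a mean difference in raw SD units (assumption).** Then d on the change scale is 0.4 / √(2(1 − ρ)), with N = 68:

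| ρ | d (SD of change) | power at 0.05 | power at 0.01 |
|---|---|---|---|
| 0.5 | 0.400 | 37% | 17% |
| 0.7 | 0.516 | 55% | 31% |
| 0.8 | 0.632 | 73% | 49% |
| 0.875 | 0.800 | 90% | 74% |

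A baseline-adjusted comparison, d = 0.4 / √(1 − ρ²), does somewhat better at 0.05: 47%, 62% and 77% at ρ = 0.5, 0.7 and 0.8, and 91% at ρ = 0.87.

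**The case against.** The strongest defence is that the Design statement is internally correct. It names G*Power and a within-between interaction, for which Cohen's f is a natural effect measure. With f = 0.4, two measurements and λ = f²N, 68 gives 90.15% at 5%. That stands. A reader might infer that 68 does not give 90% power for an effect of 0.4, but on this reading it does, so no arithmetic error is shown.

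A reader might also infer that a pooled mean difference was entered on the wrong scale. The documents do not support this. They give neither the metric nor the value of the pooled effect, and an effect that was guided by a source need not equal it. Even on the mean-difference reading, the shortfall depends on a correlation that the plan does not give, and it vanishes at 5% near ρ = 0.875.

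Nor do the three visits in the GEE show that 68 is wrong. Three measurements with f = 0.2 and ρ of about 0.38 also return 68.

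Finally, the plan openly labels results between 0.01 and 0.05 as nominal. That is candid, but it confirms that such results do not meet the significance criterion. It does not bring the stated 90% into line with that criterion. The mismatch in alpha needs no outside source and remains after all of these points.

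**Conclusion.** The point holds as a mismatch between the alpha used for sizing and the alpha used for significance, together with unstated inputs. For the effect that 68 can be shown to detect with 90% power at two-sided 5%, a difference in change of 0.8 SD of change, power at the plan's threshold is about 74%. The shortfall is about 16 percentage points. Other settings that return 68 give about 75%. These figures assume equal allocation, no loss of participants, and the repeated-measures ANOVA as an approximation to the GEE.

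The lower powers for a 0.4 SD mean difference (37% to 90% at 0.05 and 17% to 74% at 0.01, for ρ from 0.5 to 0.875) are conditional. They show why the metric has to be named; they do not establish that the plan made an error of scale.

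**What to change.** Keep N = 68 and rewrite the sample-size paragraph in the Design section:

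- State power at the alpha the analysis uses. Subject to the sponsor confirming the settings, possible wording is: *With 34 participants per arm, power to detect a between-arm difference in SRS change of 0.8 SD of change is about 74% at p ≤ 0.01 and 90% at two-sided 0.05; 90% power at 0.01 would require a difference of about 0.96 SD.*
- Have the sponsor report what was actually entered in G*Power: the effect metric, number of measurements, within-person correlation and noncentrality option. State the allocation ratio as well.
- State the metric of the pooled effect that guided 0.4, and give the power for a 0.4 SD mean difference as a range over ρ, at both 0.05 and 0.01.

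The cost is wording only: no extra participants and no change to the analysis. The downside is that the stated power becomes less favourable.
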